12.0 STATISTICAL METHODS

12.1 Sample Size Justification

The New Zealand National Joint Registry reported a mean Oxford Knee Score of 37.05 (with a standard deviation of 8.30) at 6 months following total knee arthroplasty, using mostly conventional instruments (NZOA New Zealand Joint Registry, 2010). The registry also reports the following scoring categories: Excellent >41, Good 34-41, Fair 27-33, and Poor <27.

Kamat et al. (2009) undertook a study comparing the clinical outcomes of manual versus computer-assisted surgery instrumentations systems. A 5-point change in Oxford Knee Scores at a post-operative period of 6 months was determined to be a clinically meaningful difference.

A minimum of 45 patients per group are required, based on an improvement from 37 (mean Oxford Knee Score reported in the New Zealand registry) to 42 (scoring category of excellent), with 80% power and significance level of 5%.

An additional 5 patients per group (10%) has been included into the target patient number to allow for loss to follow-up, bringing the target to 50 patients per group.

A maximum of 100 patients will be enrolled in the Extension Study.

12.2 Data Capture and Analysis

All data will be recorded on 2-part NCR paper Case Report Forms (CRFs). The surgeon will complete and sign forms at the time of completion. Original CRFs will be collected by Stryker for data entry. Copies will remain at the Investigator site. Archiving will be undertaken in accordance with ICH/GCP guidelines (Appendix 6).

Any unclear or ambiguous data will be queried and all cleaned data will be entered into a database for tracking purposes.

The primary outcome data gathered from patients in each study group will be pooled and summarized.

For the primary objective of the study, the 95% confidence interval of the difference in total Oxford Knee Score improvement (at 12 months post-operative) between the Intervention Group and the Control Group will be computed. Two and five year data will be analysed as per the 12 month data.

For secondary objectives, independent two-sample t-test or Wilcoxon non-parametric rank-sum test will be used to compare the International Knee Society Score (IKSS), Forgotten Joint Score (FJS), WOMAC, EQ-5D and VAS Pain scores between the Intervention Group and the Control Group at all available visits. Please note that the test we intend on using will be dependent on the distribution of the data collected following appropriate normality testing. Adjustments will be made for multiple testing at each level.

Independent two-sample t-test or Wilcoxon non-parametric rank-sum test will also be used to compare cost-effectiveness and cost-utility between the Intervention Group and the Control Group. As mentioned above, this will also be dependent on the distribution of the data collected.

Adverse events will be tabulated separately and reviewed for any commonalities. Revision surgery data from the Extension Study will be compared to the revision rates reported in the National Joint Registry report at 2 years and 5 years. A cost benefit analysis will be undertaken with the use of data from the Australian Government Hospital Casemix Protocol Annual Report.

A formal interim analysis will take place following completion of the ShapeNZRCT-10 study (12 month visit). Additionally, formal interim analyses will take place following all participants' completion of the 2 year visit and again following completion of all participants' 5 year follow-up visits.

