3.0 OBJECTIVES

The primary objective of this study is:

• To demonstrate, through calculation of Oxford Knee Score at 12 months postoperative, that total knee replacement (TKR) performed using the ShapeMatch® Cutting Guide provides improvement from preoperative levels of patient pain and function comparable to the improvement obtained with TKR performed using computer-assisted Navigation. Oxford Knee Scores will be calculated pre-operatively and at 6 weeks, 6 months and 12 months post-operatively.

The secondary objectives of this study are:

- The efficacy objective is to compare radiographic, pain, function and health-related quality of life (QOL) between the ShapeMatch® Cutting Guide group and the computer-assisted Navigation control group. This objective will be achieved by utilizing the following instruments pre-operatively and at the 6-week, 6-month and 12 month visits:
 - Perth CT protocol
 - AP and ML X-rays
 - Oxford Knee Score
 - The International Knee Society Score (IKSS)

- The Forgotten Joint Score (FJS-12)
- WOMAC
- EQ-5D-3L
- VAS Pain
- To compare the cost-effectiveness and cost-utility of the procedure between the ShapeMatch[®] Cutting Guide group and the computer-assisted Navigation control group. This objective will be assessed by recording and calculating the following parameters:
 - o Wound length
 - Total duration of operating procedure (anaesthetic time and skinto-skin incision time)
 - o Cost of consumable items used during operating procedure
 - Length of stay in hospital
 - o Quality-adjusted life-years (QALYs) from EQ-5D-3L

The hypothesis is that there is a statistically significant improvement in functional outcome 12 months following a primary Total Knee Replacement when kinematic limb alignment (using ShapeMatch® Cutting Guide) is used compared to that resulting from a goal of neutral mechanical axis alignment (using computer-assisted Navigation).

The Extension Study Primary Objective is:

To determine the clinical and radiographic outcomes at 2 years and 5 years post-surgery, in patients receiving a Stryker Triathlon[®] Total Knee System for Total Knee Arthroplasty (TKA) implanted using either Stryker OtisMed[®] ShapeMatch[®] Technology (intervention) or Stryker PrecisioN v4.0 Knee Navigation (control).

The Extension Study Secondary Objectives are:

 To determine the revision rate, device-related adverse events and reoperation rates.

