18.0 MODIFICATION OF PROTOCOL

No changes to this Protocol will be permitted without the written approval of the applicable Ethics Committee.

Protocol deviation details including the type of deviation (E.g. informed consent, inclusion/exclusion criteria, treatment, tests not performed and follow-up) should be

recorded on a Protocol Deviation Form as soon as identified and notification will be made to the applicable Ethics Committee according to the Ethics Committee requirements.

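### The 80% power is derived for an attained score, but the primary analysis uses improvement from pre-op with no baseline adjustment; naming pre-op Oxford Knee Score as a covariate closes the gap

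*Combined protocol and SAP*

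**What the plan says.** Section 12.1 (Sample Size Justification) starts from a registry figure, "a mean Oxford Knee Score of 37.05 (with a standard deviation of 8.30) at 6 months following total knee arthroplasty". It then says "A minimum of 45 patients per group are required, based on an improvement from 37" to 42, at 80% power and a 5% significance level. Both 37 and 42 are post-operative score levels, so the 5 points is a gap between two attained means. Five patients per group are added for loss to follow-up, giving 50.

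Section 12.2 (Data Capture and Analysis) defines the primary analysis as "the 95% confidence interval of the difference in total Oxford Knee Score improvement (at 12 months post-operative") between the two groups. Section 3.0 (Objectives) fixes the reference point: the new technique is to be shown to be one that "provides improvement from preoperative levels of patient pain and function comparable to the improvement obtained with TKR performed using computer-assisted Navigation". Improvement in the analysis is therefore measured from the pre-operative score.

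Section 12.2 names no model and no covariate for this interval. The only between-group tests it names, for the secondary outcomes, are unadjusted two-sample tests. The pre-operative score will be available: "Oxford Knee Scores will be calculated pre-operatively and at 6 weeks, 6 months and 12 months post-operatively".

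**The concern.** The word improvement covers two different variables. In section 12.1 it is a difference between post-operative means. In section 12.2 it is each patient's change from before surgery. Randomisation makes the expected 5-point treatment difference the same for both, but not the SD. The SD of a change score depends on the pre-operative SD and on the correlation between the pre-operative and 12-month scores, and the documents give neither.

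If that correlation is low, subtracting the baseline adds noise. The primary comparison then has less than its stated power, and the planned 95% interval is wider than section 12.1 implies. If it is high, power exceeds 80%. As written, a reader cannot tell which applies.

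**Working it through.** **Inputs from the documents (section 12.1).** SD 8.30 (attained score, 6 months); difference 5; power 80%; significance level 5%; 45 evaluable per group. The level is taken as two-sided, to match the 95% interval; a one-sided calculation gives 35 per group, which does not match.

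**Assumptions.** The documents do not give the 12-month SD (SD1), the pre-op SD (SD0) or their correlation (r). SD1 is set to 8.30 unless stated, and the other two are varied.

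**1. The plan's own figure.** Two-sample t, noncentral t distribution. At 45 per group the noncentrality is 5 / (8.30 × √(2/45)) = 2.86. Power is 79.8% at 44, 80.7% at 45 and 84.7% at 50 per group. The stated 45 is reproduced, using the SD of the attained score.

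**2. Largest SD that keeps 80% at 45 per group.** Solving for the SD gives 8.37.

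**3. Condition for the change score.** SD(change) = √(SD0² + SD1² − 2·r·SD0·SD1). Setting this to at most 8.37 gives

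r ≥ (SD0² + SD1² − 8.37²) / (2·SD0·SD1).

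For SD0 = SD1 = 8.30: (68.89 + 68.89 − 70.10) / 137.78 = 0.49. For SD0 = 6.0, 7.0 and 10.0 the result is 0.35, 0.41 and 0.60. Each is close to SD0 / (2·SD1). If all 50 per group are evaluable, the threshold at SD0 = 8.3 is 0.43.

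**4. Power at 45 per group, true difference 5, SD1 = 8.30.** For the adjusted analysis (ANCOVA) the residual SD is 8.30 × √(1 − r²), with 87 degrees of freedom; it does not depend on SD0.

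| r | Change, SD0 = 6.0 | Change, SD0 = 7.0 | Change, SD0 = 8.3 | Change, SD0 = 10.0 | ANCOVA |
|---|---|---|---|---|---|
| 0.2 | 72.1% | 67.4% | 60.8% | 52.2% | 82.2% |
| 0.3 | 77.3% | 73.1% | 66.6% | 57.5% | 84.2% |
| 0.4 | 82.9% | 79.3% | 73.2% | 64.0% | 86.9% |
| 0.5 | 88.5% | 85.9% | 80.7% | 71.6% | 90.4% |
| 0.6 | 93.7% | 92.2% | 88.5% | 80.5% | 94.2% |
| 0.7 | 97.7% | 97.3% | 95.4% | 89.8% | 97.7% |

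At r = 0, ANCOVA gives about 81%, the section 12.1 figure. At r = 0.3, 80% power needs 54, 62 or 76 per group with change scores (SD0 = 7.0, 8.3, 10.0) and 41 with ANCOVA.

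**5. Width of the planned interval (SD0 = 8.3, 45 per group).** Half-width = t × SD × √(2/45).
- r = 0.3: change 1.987 × 9.82 × 0.2108 = 4.11 points; ANCOVA 1.988 × 7.92 × 0.2108 = 3.32 points.
- r = 0.5: 3.48 and 3.01 points.

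**6. If the 12-month SD is 9.0 instead.** ANCOVA power is 74, 76, 78, 81 and 85% at r = 0, 0.2, 0.3, 0.4 and 0.5. Change-score power with SD0 = 9.0 is 54, 60, 66 and 74% at r = 0.2 to 0.5. The largest 12-month SD at which ANCOVA keeps 80% is 8.37 at r = 0, 8.78 at r = 0.3 and 9.67 at r = 0.5.

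**7. Same quantity estimated.** With pre-op score in the model, the treatment coefficient is algebraically identical whether the outcome is the 12-month score or the improvement; only the baseline slope shifts, by 1. In simulated data the two coefficients agreed to within 1e-12.

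**The case against.** The strongest reply is that no shortfall is shown. Every figure below 80% rests on an assumed correlation and pre-op SD. Once r reaches 0.6, change scores have at least 80% power at all four pre-op SDs tabulated, and with all 50 per group evaluable the threshold is lower. Comparing change scores in a randomised trial is unbiased, and section 12.2 does not actually rule out adjustment. This stands as a limit on the claim: the defect is an undisclosed condition, not a proven loss of power. It does not rescue section 12.1, because the plan offers nothing to show that the condition is met, and its 80% is tied to 45 patients, with the other five reserved for loss to follow-up.

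Second, adjustment does not by itself secure 80%. That is right: carrying a 6-month registry SD to 12 months is a separate assumption, and at SD 9.0 the adjusted analysis falls below 80% for r up to 0.3. Adjustment removes only the dependence on the correlation.

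Third, power to detect 5 points presupposes the superiority hypothesis, whereas the primary objective in section 3.0 speaks of comparability and section 12.2 gives no margin. That conflict is not settled here. A narrower interval is useful under either reading.

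Finally, the 45 was computed without adjustment and should not be relabelled as an adjusted calculation. The wording proposed below respects this.

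**Conclusion.** The concern holds. The stated 80% belongs to a comparison of attained scores with SD 8.30. For an unadjusted comparison of improvement at 45 per group it needs a pre-op/12-month correlation of at least about 0.35 to 0.60, for pre-op SDs from 6.0 to 10.0 and a 12-month SD of 8.30. Below that threshold power drops, for example to 67% at r = 0.3 with equal SDs; above it, power exceeds 80%. With pre-op score as a covariate, power is about 81% or more at every correlation if the 12-month SD is 8.30, and asymptotically the estimate is never less precise than the change score.

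This is a point the plan should address, not an invalid analysis: an unsupported power statement together with an avoidable loss of precision in the primary interval.

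**What to change.** In section 12.2, keep the quantity and name the model:

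> The between-group difference in 12-month Oxford Knee Score improvement and its 95% confidence interval will be estimated from a linear model of 12-month score on treatment group and pre-operative score.

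The existing sentence "Two and five year data will be analysed as per the 12 month data" carries the model to the extension visits.

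In section 12.1, add that:
- the 45 per group was derived for an unadjusted comparison of attained scores;
- the adjusted comparison is expected to have at least that power at the same SD;
- the figure assumes that the 6-month registry SD of 8.30 also holds at 12 months. Give the power at a larger SD, for example 74 to 81% at SD 9.0 for r = 0 to 0.4.

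Secondary scores need no change. Adjusting IKSS, WOMAC, EQ-5D and VAS Pain for baseline is optional and should keep the non-parametric alternative; FJS-12 has no pre-operative value.

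The cost is a short addition to each section, filed as an amendment, since section 18.0 says "No changes to this Protocol will be permitted without the written approval of the applicable Ethics Committee". No new patients, visits or data are needed.

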6.2 Exclusion Criteria

- The patient has a history of total, unicompartmental reconstruction or fusion of the affected joint.
- Patient has had a previous osteotomy around the knee.
- The patient is morbidly obese (BMI ≥ 40).
- The patient has a deformity which will require the use of stems, wedges or augments in conjunction with the Triathlon Total Knee System.
- The patient has a varus/valgus malalignment ≥ 15° (relative to mechanical axis).
- The patient has a fixed flexion deformity ≥ 15°.
- The patient has a neuromuscular or neurosensory deficiency, which would limit the ability to assess the performance of the device.
- The patient has a systemic or metabolic disorder leading to progressive bone deterioration.
- The patient is immunologically suppressed or receiving steroids in excess of normal physiological requirements.
- Patient has a cognitive impairment, an intellectual disability or a mental illness.
- The patient is pregnant.
- The patient has metal hardware present in the region of the hip, knee or ankle (as this is known to create geometrical distortion in the region of the implant).
- The patient has any known contraindications for undergoing assessment by MRI (e.g. ferrous implants, metallic clips, magnetically activated implanted devices such as cardiac pacemakers, etc.).

6.3 Extension Study: Inclusion Criteria (applicable to patients electing to continue participation in the Extension Study)

- Patient was enrolled in ShapeNZRCT-10 and completed either the 6 month or 12 month follow-up visit (or both).
- Patient is willing and able to give informed consent to participate in the study.
- Patient is willing and able to comply with the specified clinical and radiographic evaluations.

6.4Extension Study: Exclusion Criteria (applicable to patients electing to continue participation in the Extension Study)

- Patient no longer has the Triathlon[®] Total Knee System in situ, including patients that have had revision surgery.
- Patient has a cognitive impairment, an intellectual disability or a mental illness that is considered by the investigator to inhibit the patient's capacity to consent to research and the ability to participate in it.
- Patient no longer resides in a geographical location that would reasonably permit clinic visits at protocol specified intervals.

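### Section 12.2 has no analysis that uses the 6-week or 6-month Oxford Knee Score, and the 12-month primary comparison by default drops patients without a 12-month score

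*Combined protocol and SAP*

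**What the plan says.** **Collection.** Section 3.0 states: "Oxford Knee Scores will be calculated pre-operatively and at 6 weeks, 6 months and 12 months post-operatively". The evaluation schedule in Section 1.0 agrees.

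**Objectives.** Section 3.0 names the OKS twice: as the primary outcome at 12 months, and in the list of instruments for the secondary between-group comparison, of which it says "This objective will be achieved by utilizing the following instruments pre-operatively and at the 6-week, 6-month and 12 month visits".

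**Analysis.** For the primary objective Section 12.2 computes "the 95% confidence interval of the difference in total Oxford Knee Score improvement (at 12 months post-operative") between the two groups. Two-sample tests are planned for the secondary scores, "International Knee Society Score (IKSS), Forgotten Joint Score (FJS), WOMAC, EQ-5D and VAS Pain scores between the Intervention Group and the Control Group at all" (each visit with data). The OKS is not in that list. For the extension, "Two and five year data will be analysed as per the 12 month data". Section 12.2 also says that primary outcome data will be pooled and summarised, without giving a method.

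**Loss.** Section 12.1 says: "An additional 5 patients per group (10%) has been included into the target patient number to allow for loss to follow-up". Section 6.3 admits to the extension a patient who "completed either the 6 month or 12 month follow-up visit (or both"). Under Section 1.0 a visit outside its window counts as missed. Re-operation ends participation (Section 17.2), and so does unblinding (Section 17.3). No section names a repeated-measures model, an imputation method, a missing-data rule or an analysis set.

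**The concern.** The primary comparison uses one post-operative visit. A patient with 6-week and 6-month scores but no 12-month score has no 12-month improvement and contributes nothing, although the 6-month score is likely to be a good predictor of the missing value. Section 6.3 allows for such patients.

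Two things are at stake. The first is precision: information already in the database is unused. The second is bias: if patients who recover poorly stop attending more often in one arm, the completers in that arm look better than the arm as randomised. The extra five patients per group restore the number of completers but do nothing about selective loss.

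There is also a mismatch within the plan. Section 3.0 sets an objective for the early OKS that Section 12.2 gives no method to meet.

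**Working it through.** **Inputs from the documents.** Section 12.1 gives a "mean Oxford Knee Score of 37.05 (with a standard deviation of 8.30) at 6 months following total knee arthroplasty", a target difference of 5 points (37 to 42), 80% power, 5% significance, 45 per group, and 50 per group after a 10% allowance. The documents give no correlation between visits and no SD of improvement. The values used below for these are assumptions.

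**1. The plan's own figure.** n = 2(1.96 + 0.842)² × 8.30² / 5² = 43.3, so 44 per group by the normal approximation. With the t distribution, 44 per group gives 79.8% power and 45 gives 80.7%, so the stated 45 reproduces for a two-sided test. Also 45 / 0.90 = 50, as stated.

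**2. Precision.** Let q be the share of an arm with a 6-month but no 12-month score, lost at random, and ρ the correlation between the two visits. A model that uses the 6-month score estimates the 12-month mean with variance (SD²/50) × [ρ² + (1 − ρ²)/(1 − q)]. Its effective sample size is 50 divided by the bracket. Worked example with q = 0.10, ρ = 0.7: 0.49 + 0.51/0.90 = 1.0567, and 50/1.0567 = 47.3 against 45 completers. With SD 8.30 and ρ from 0.5 to 0.85 (normal approximation):

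| Loss | Completers per arm | Power, completers only | Effective n with 6-month score | Power | CI half-width |
|---|---|---|---|---|---|
| 10% | 45 | 81.5% | 46.2 to 48.5 | 82.5% to 84.3% | 3.43 falls to 3.39–3.30 |
| 20% | 40 | 76.9% | 42.1 to 46.8 | 78.9% to 83.0% | 3.64 falls to 3.55–3.36 |

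The gain is 1 to 3 power points at 10% loss and 2 to 6 at 20%.

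To separate this from the gain due to the pre-operative covariate, compare with a covariate-adjusted complete-case analysis, assuming a pre-operative correlation of 0.4:
- Residual SD: 8.30 × √(1 − 0.16) = 7.61.
- For ρ = 0.7 to 0.85, the 6-to-12-month correlation given the pre-operative score is (ρ − 0.16)/0.84 = 0.64 to 0.82.
- At 10% loss, the same variance formula raises power from 87.7% to 89.0–89.8%, a gain of 1 to 2 points.
- Simulation gave 1 to 3 points at 10% random loss. At 25% loss, an illustrative figure for the extension, one simulation had power rising from 79% to 83–86% and another a gain of 5 to 6 points.

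**3. Bias when loss depends on the 6-month score in one arm only.** Let s be the amount, in SD units, by which the retained patients' mean 6-month score exceeds the mean of all patients in that arm. The bias in the 12-month score is ρ × s × 8.30. For improvement, the planned measure, the pre-operative score is partly selected too, so the bias is (ρ − 0.4) × s × 8.30.
- *Moderate selection* (odds of loss double per SD lower score). At 10% loss and ρ = 0.7 the simulated bias in the 12-month score is 0.39, so s = 0.39/(0.7 × 8.30) = 0.067. For improvement this gives 0.30 × 0.067 × 8.30 = 0.17 (ρ = 0.7) and 0.45 × 0.067 × 8.30 = 0.25 (ρ = 0.85). At 20% loss, s = 0.75/(0.7 × 8.30) = 0.129, giving 0.32 and 0.48.
- *Range across simulations* of the planned comparison: about 0.2 to 0.4 points at 10% loss and 0.3 to 0.6 at 20%. The longitudinal model had bias of about 0, as it must when loss depends only on observed scores.
- *Extreme selection* (every patient lost from that arm is among its lowest scorers). At 10% loss s = 0.1755/0.90 = 0.195, giving 0.30 × 0.195 × 8.30 = 0.49 to 0.45 × 0.195 × 8.30 = 0.73 points on improvement.

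**4. Same loss mechanism in both arms.** With a true 5-point difference and about 10% loss overall, the simulated difference in 12-month scores is 4.84 to 4.90. With no arm difference there is no bias.

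**5. Type I error of the planned comparison.** The SD of improvement is 8.30 × √[2(1 − 0.4)] = 9.09, so the standard error with 45 per arm is 9.09 × √(2/45) = 1.92. A bias of 0.2 to 0.4 gives a two-sided error of 5.1% to 5.5%. At 20% loss (standard error 2.03, bias 0.4 to 0.6) it is 5.4% to 6.0%.

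**The case against.** The strongest reply is that this is a drafting gap with a small effect. Section 3.0 does plan an early OKS comparison. Section 12.2 states no complete-case rule. Sections 16.0 and 21.2 require attempts to recover incomplete data, and the 12-month window is two months either side. Patients are blinded, which makes arm-specific loss less likely. The design already budgets for 45 completers per group.

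Much of this stands, and it rules out several stronger readings:
- *That the plan ignores the early OKS altogether.* Section 3.0 contradicts this. What is missing is a method in Section 12.2.
- *That the plan prescribes exclusion.* Exclusion follows from the definition of the measure and the plan's silence, and is not written down.
- *That complete cases are unbiased only if loss is unrelated to early outcome.* That condition is sufficient but not necessary, as step 4 shows.
- *That type I error is materially inflated.* A figure as high as 8.2% arises in simulation for a covariate-adjusted complete-case model, which the plan does not use. The planned comparison stays near 5% to 6%.
- *That the allowance for loss is wrong.* It is arithmetically correct, and 45 completers keep 80% power on the plan's SD. That SD describes a 6-month score, however, so the margin is not assured for improvement.

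The reply does not remove the point. A visit-by-visit test of the early OKS would still leave patients without a 12-month score out of the primary comparison, and silence leaves the handling of missing scores to be chosen after the data are seen. One objection also limits the remedy: a missing-at-random model gives no guarantee for patients who leave after re-operation or unblinding, because those events may follow the last recorded score.

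**Conclusion.** The point holds as a modest but worthwhile improvement. Section 12.2 specifies no analysis of the 6-week or 6-month OKS, and the primary comparison loses by default any patient without a 12-month score.

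At 10% loss this costs about 1 to 3 power points and, if low scorers leave one arm only, a bias of roughly 0.2 to 0.4 points. That is small beside the 5-point target and a confidence interval half-width of about 3.4. It is larger at 20% to 25% loss. The documents do not predict such loss, but it could occur at 2 and 5 years, where fresh consent is needed and revised patients are excluded from entry.

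The sizes rest on SD 8.30 at every visit, assumed correlations (0.4 with the pre-operative score, 0.5 to 0.85 between 6 and 12 months) and assumed drop-out patterns. The gap itself does not depend on them. The documents do not support a claim that the 12-month result would be seriously biased or the trial underpowered for this reason.

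**What to change.** In Section 12.2:
- Estimate the primary 12-month OKS difference and its 95% confidence interval from a repeated-measures model of the 6-week, 6-month and 12-month scores in all randomised patients. Include arm-by-visit effects, the pre-operative OKS as covariate (or a common pre-operative mean), unstructured covariance with a stated fallback if it does not converge, and Kenward-Roger degrees of freedom.
- Fix the 12-month result on data up to 12 months only. Extend the model to 2 and 5 years in separate later analyses, so that later data cannot change the primary estimate.
- Report the early-visit OKS differences from the same model, which supplies the method that the Section 3.0 objective lacks.
- Add a missing-not-at-random sensitivity analysis covering patients who leave after re-operation, revision or unblinding.
- If the approach is carried over to other scores, leave out the pre-operative term for the FJS-12, which has no pre-operative measurement.

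The cost is about one paragraph and slightly more programming, with no new visits or data. The downside is that the primary estimate then relies on a missing-at-random assumption, which the sensitivity analysis is there to test.
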